It can sometimes be challenging to determine if a wart is completely clear after treatment due to ongoing local skin reactions. At any visit where the investigator is unable to evaluate or treat some warts due to ongoing local skin reactions, an "Unscheduled" Visit should be documented. The timing of the next visit will be determined by the resolution of the local skin reaction. A Treatment Visit should be documented at every visit where Study drug is applied. Treatment should only take place at a visit when all warts are evaluable (i.e., not obscured by an ongoing LSR) and all warts that are not completely clear, should undergo treatment with Study drug. No partial treatment of warts is permitted.

For Cohort 2, Study drug is to be applied to the wart site on any Treatment Visit where a new clinical assessment of complete clearance is made for that wart (*e.g., if a patient returns for Treatment Visit 2 and is clinically assessed to have no visible evidence of remaining wart, then Study drug is to be applied to this wart site at Treatment Visit 2. However, if the patient remains completely clear at that wart site when returning for Treatment Visit 3, then no Study drug would be applied at Treatment Visit 3.*) Should it become clear that the subject will be unable to complete the EOS visit within the allowed window of Day 84 (- 0/+ 8) days, the subject should be brought in for their EOS visit as soon as they are able. This will be documented as a protocol deviation.

In instances where the clinician can adequately assess the treatment sites but is uncertain if residual wart is remaining, treatment should be applied, and the subject should return for evaluation per protocol. Treatment visits and assessments are to take place in order (e.g., Treatment 1, Treatment 2, Treatment 3 and Treatment 4). Subjects that receive fewer than 4 treatments within the 63-day (Cohort 1) or 75-day (Cohort 2) treatment period, due to the duration of post-treatment local skin reactions, will not be considered a protocol deviation. No treatment should be administered after the 63-day treatment period in Cohort 1 or the 75-day treatment period in Cohort 2 without Sponsor's approval.

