9.2.7 Handling of Missing data

Clearance of all treatable warts is to be assessed at each Treatment Visit as well as unscheduled visits over the duration of the study. The assessment done at the EOS Visit (Day 84) will be considered to be the primary efficacy endpoint.

Subjects who do not have an assessment of complete clearance of all treatable warts at the EOS Visit (Day 84) will be considered to have missing data for the primary endpoint. The primary method to handle missing data will be to assign all subjects with missing complete clearance data as not having achieved complete clearance.

The procedures for handling missing data for other study endpoints will be described in the statistical analysis plan.

9.3 Informed Consent/Assent and Authorization for Use and Disclosure of Protected Health Information

Written assent and informed consent and authorization of use and disclosure of protected health information must be obtained from each subject (or the subject's legally acceptable representative) before performing any study-specific screening/baseline period evaluations. One copy of the signed informed consent form (and IRB-required assent form) and authorization for use and disclosure of protected health information form will be given to the subject, and the investigator will retain the original. The informed consent/assent form and authorization for use and disclosure of protected health information, which is prepared by the investigator or the site, must have been reviewed and approved by the sponsor, the study monitor, and the investigator's IRB and privacy board (if separate from the IRB) before the initiation of the study. The informed consent form must contain the 20 elements of informed

consent described in International Council for Harmonisation E6, Section 4.8. The authorization for use and disclosure of protected health information must contain the elements required by Title 45 of the Code of Federal Regulations, Section 164.508(b), and any local regulations for valid authorizations.

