It can sometimes be challenging to determine if a wart is completely clear after treatment due to ongoing local skin reactions. At any visit where the investigator is unable to evaluate or treat some warts due to ongoing local skin reactions, an “Unscheduled” Visit should be documented. The timing of the next visit will be determined by the resolution of the local skin reaction. A Treatment Visit should be documented at every visit where Study drug is applied. Treatment should only take place at a visit when all warts are evaluable (i.e., not obscured by an ongoing LSR) and all warts that are not completely clear, should undergo treatment with Study drug. No partial treatment of warts is permitted.

For Cohort 2, study drug is to be applied to the wart site on any Treatment Visit where a new clinical assessment of complete clearance is made for that wart (e.g., if a patient returns for Treatment Visit 2 and is clinically assessed to have no visible evidence of a remaining wart, then Study drug is still to be applied to this wart site at Treatment Visit 2. However, if the patient remains completely clear at that wart site when returning for a subsequent visit such as Treatment Visit 3, then no Study drug would be applied at Treatment Visit 3.) Should it become clear that the subject will be unable to complete the EOT visit within the allowed window of Day 84 (+/- 8) days, the subject should be brought in for their EOT visit as soon as they are able. This will be documented as a protocol deviation.

In instances where the clinician can adequately assess the treatment sites but is uncertain if a residual wart is remaining, treatment should be applied, and the subject should return for evaluation per protocol. Treatment visits and assessments are to take place in order (e.g., Treatment 1, Treatment 2, Treatment 3 and Treatment 4). Subjects that receive fewer than 4 treatments within the 75-day (Cohort 2) treatment period, due to the duration of post-treatment local skin reactions, will not be considered a protocol deviation. No treatment should be administered after the 75-day treatment period in Cohort 2 without Sponsor’s approval.

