On the Wart Location and Measurement case report form (CRF), wart information is collected for each individual wart. For the purpose of efficacy analysis, clearance of each wart needs to be determined using results collected on this page. A wart will be considered to have cleared for a particular visit when a wart is reported to have a diameter of 0 mm at that visit. Should a wart return after initial clearance, a diameter > 0 mm will be recorded, and the wart will not be considered cleared at that visit. Otherwise,

if the wart does not return, the check box “Wart has cleared” will be marked for subsequent visits. For the purpose of analysis, the wart will be counted as cleared at all visits where “Wart has cleared” has been marked.

Some efficacy endpoints will be summarized by treatment visit. Treatments are planned to occur every 21 days as long as warts are present for up to 4 treatments within the 75 day treatment period. Treatment may be delayed for various reasons including, but not limited to, ongoing local skin reactions (e.g. scabbing). As a result, the timing of when subjects receive treatment may vary. For the purpose of naming treatment visits, only visits when treatment was given or the check box “Wart has cleared” for all warts will be considered. Using this method, Treatment Visit 1 will be the 1st visit treatment was applied; Treatment Visit 2 will be the 2nd visit treatment was applied, etc. Visits when treatment was planned to be given but treatment was not applied or clearance was not achieved will be recorded as “Unscheduled”.

For results to be considered for any by visit analyses, visits must be within visit windows as described in this section of the analysis plan. Results that are collected between Day 11 and Day 157 will be assigned to visits according to the visit windows described below, regardless of the name of the visit. Should two or more results be collected within a specific visit window, the visit closest to the planned day with a non-missing value will be used for analysis. Results from visits that occur outside the visit windows will not be considered for analysis, but will be included in study listings. The visit windows to be considered are as follows:

- Day 21- visit falls +/- 10 days from planned visit study day (i.e., between Day 11 and Day 31)
- Day 42- visit falls +/- 10 days from planned visit study day (i.e., between Day 32 and Day 52)

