- Day 63- visit falls +/- 10 days from planned visit study day (i.e., between Day 53 and Day 73)
- End of Treatment (EOT) Visit- visit falls +/- 10 days from planned visit study day (i.e., between Day 74 and Day 94)
- Day 105- visit falls +/- 10 days from planned visit study day (i.e., between Day 95 and Day 115)
- Day 126- visit falls +/- 10 days from planned visit study day (i.e., between Day 116 and Day 136)
- Day 147- visit falls +/- 10 days from planned visit study day (i.e., between Day 137 and Day 157)

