8.4.1. Handling of Missing Data for Complete Clearance Endpoint

The efficacy endpoint, proportion of subjects exhibiting complete clearance of all treatable warts, is to be assessed during the study. Assessments are to be done at Treatment Visit 2, Treatment Visit 3, Treatment Visit 4, the EOT visit and follow-up visits at Day 105, Day 126 and Day 147.

Subjects who do not have an assessment of complete clearance of all treatable warts in a particular visit window for any of the scheduled assessments will be considered to have missing data for this endpoint at that visit. The primary method to handle missing data will be to assign all subjects with missing clearance data as not having achieved complete clearance. For additional considerations related to assessments of clearance, see Section 8 (Efficacy Analysis).

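### Cohort 2: an end-of-treatment reading taken on Day 95 or later is moved out of the primary window, so an observed clearance can be scored as not cleared

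*Protocol*

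**What the plan says.** The SAP covers Cohort 2 only, so the point is confined to that cohort.

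- **Visit instruction.** Protocol section 4.1 deals with a subject "unable to complete the EOS visit within the allowed window of Day 84 (- 0/+ 8) days" and says that "the subject should be brought in for their EOS visit as soon as they are able. This will be documented as a protocol deviation". The visit is labelled EOS there, but Day 84 with that window is the Cohort 2 EOT visit. No latest day is set. SAP section 3 carries the instruction over, stating that "the subject should be brought in for their EOT visit as soon as they are able", but it words the condition with a different window, for a subject "unable to complete the EOT visit within the allowed window of Day 84 (+/- 8) days".
- **Assignment of readings.** Under SAP section 8, readings from Day 11 to Day 157 "will be assigned to visits according to the visit windows described below, regardless of the name of the visit". The window for the primary endpoint is "End of Treatment (EOT) Visit- visit falls +/- 10 days from planned visit study day (i.e., between Day 74 and Day 94"). When two readings share a window, the one nearer the planned day is used.
- **Missing data.** SAP 8.4.1 treats an empty visit window as missing clearance data, and "The primary method to handle missing data will be to assign all subjects with missing clearance data as not having achieved complete clearance". Protocol 9.2.7 defines missing by the visit, not by an analysis window: "Subjects who do not have an assessment of complete clearance of all treatable warts at the EOS Visit (Day 84").
- **Per Protocol population.** SAP section 6 requires, among other things, that clearance was assessed at the EOT visit and that there was no major protocol violation.

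**The concern.** The trial asks sites to hold a late EOT visit and record it, but the analysis rule has no place for the result in the primary endpoint once the visit falls after Day 94. A subject examined in person and found clear can then be counted as a failure by imputation, because the window looks empty.

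The primary endpoint is a simple proportion. The protocol synopsis says that the clearance rates are meant to support assumptions for later placebo-controlled trials. Replacing an observed clearance by an imputed failure pulls that estimate down, and readers of the table would take the subject for one who was not assessed.

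**Working it through.** **1. Windows.** The plan's own EOT window is reproduced: 84 - 10 = 74 and 84 + 10 = 94. Applying +/- 10 days to Days 21, 42, 63, 84, 105, 126 and 147 gives seven windows that join without gaps from Day 11 to Day 157.

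| Source | Range for the EOT visit |
|---|---|
| Protocol 4.1 (-0/+8) | Day 84 to 92 |
| SAP 3 (+/-8) | Day 76 to 92 |
| SAP 8, analysis (+/-10) | Day 74 to 94 |

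**2. Where a late EOT reading goes.**

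| Day of EOT visit | Window under SAP 8 |
|---|---|
| 93 to 94 | EOT (late under the protocol, still counted) |
| 95 to 115 | Day 105 |
| 116 to 136 | Day 126 |
| 137 to 157 | Day 147 |
| 158 or later | none, listing only |

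**3. Whether the reassigned reading is used.** Follow-up visits have a protocol window of +/- 4 days, so a Day 105 visit held in window falls on Day 101 to 109, at most 4 days from Day 105. An EOT reading on Day 95 to 100 lies 105 - 100 = 5 to 105 - 95 = 10 days away. The follow-up visit is always nearer, so the EOT reading enters no by-visit analysis. If the Day 105 visit is missed, or the EOT reading falls on Day 101 or later, it can become the Day 105 result.

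**4. What the primary endpoint records.** Take a subject whose EOT visit is on Day 97 and who is clear.

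- With no other clearance reading on Day 74 to 94, the window is empty and SAP 8.4.1 gives not cleared.
- With another reading in that range, such as a Treatment Visit 4 assessment on Day 74 or 75, that reading is used. Nothing is imputed, but the EOT visit itself still does not count.
- In the first case the subject's EOT wart count is carried forward from an earlier visit (SAP 8.4.2), although a later count was taken.
- The subject can also satisfy the Per Protocol condition of an EOT assessment, unless the late visit is classed as a major deviation.

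**5. Size.** Cohort 2 is planned at about 35 subjects. If k clear subjects are affected, the rate falls by k/35.

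| k | Fall in rate (percentage points) |
|---|---|
| 0 | 0 |
| 1 | 2.9 |
| 2 | 5.7 |
| 3 | 8.6 |

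The values of k are assumptions, since the documents give no number. For scale, with an assumed count, 17/35 = 48.6% (exact 95% CI 31.4 to 66.0) compares with 18/35 = 51.4% (34.0 to 68.6).

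**The case against.** Windowing by study day is a legitimate choice, set in advance and conservative here. Section 4.1 orders the visit and logs a deviation; it does not promise that the reading will count as Day 84. Collecting late data without treating it as Day 84 is coherent. Warts can also resolve spontaneously (protocol 2.1), and in a single-arm, open-label study a later reading allows more time for that. The study is descriptive, and one subject moves the rate by far less than the half-width of the interval, about 17 points. These arguments stand as reasons for modest weight and for showing the result under the present rule. They do not explain why an observed outcome should appear as an imputed failure, given that the window already accepts readings 10 days early.

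Some stronger readings are tempting but not supported:

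- **The late reading is discarded.** It is reassigned. It goes unused only if a reading nearer the planned day exists in the new window, or if it falls after Day 157.
- **The subject is automatically a failure.** This requires that there be no other clearance reading on Day 74 to 94.
- **The SAP contradicts protocol 9.2.7.** That section gives no analysis window and does not say whether a late visit qualifies. It leaves a gap.
- **Subjects with prolonged skin reactions are the most affected.** The rule on unscheduled visits is written around treatment visits. A reading pushed to Day 95 would need warts obscured for 95 - 75 = 20 days after the last dosing day allowed without sponsor approval, or 95 - 63 = 32 days after a Day 63 dose. Protocol 2.4 regards 21 days as allowing time for reactions to resolve. Nothing shows who would attend late.
- **Early visits suffer the same loss.** The window opens 10 days before Day 84, and protocol 8.2 counts subjects who do not complete the study as failures by intention.

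**Conclusion.** The point holds for Cohort 2 in a conditional form. An EOT reading on Day 95 or later cannot supply the primary endpoint, and a subject with no other clearance reading on Day 74 to 94 is scored not cleared although the outcome was observed. The error, where it occurs, runs one way: it lowers the clearance rate, by 2.9 points per clear subject affected if 35 are analysed. How many EOT visits will fall after Day 94, and how many of those subjects will be clear, are not in the documents; the total effect may be zero. This is a mismatch between a visit instruction and an analysis window, not an arithmetical error. It is worth correcting because the remedy is cheap.

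**What to change.** In SAP sections 8 and 8.4.1:

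1. Keep the Day 74 to 94 window, so every reading that now counts remains valid.
2. Where a visit recorded as EOT is held after Day 94 and before the subject's first follow-up visit, use that reading for the EOT primary endpoint and do not reassign it.
3. Impute not cleared only when there is neither an in-window reading nor such a late EOT reading.
4. Report two sensitivity analyses: one under the present Day 74 to 94 rule, with late EOT readings not counted, and one limited to EOT visits on Day 84 to 92.

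The cost is SAP wording and two tables. No visit or data collection changes, and the late visits are already logged as deviations. The downside is that a few primary readings come later than planned, with extra time for spontaneous resolution. A late visit held before the Day 105 visit window opens on Day 101 is at most 100 - 84 = 16 days after Day 84. The delay could be longer if the late visit falls inside that window ahead of the follow-up visit, or if the Day 105 visit is late or missed. The two sensitivity analyses show how much depends on this.

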4.2 Study Population

Cohort 1 will enroll and treat a minimum of 20 subjects, 2 years of age and older, presenting with 1-6 common warts with the goal of approximately 20 subjects completing all study activities per protocol. Cohort 2 will utilize up to 4 sites to enroll approximately 35 subjects (12 years and older). Eligibility to participate in the study will be determined by the investigator on the basis of the inclusion and exclusion criteria.

4.2.1 Inclusion Criteria

To qualify for inclusion in this study, subjects must:

1. Be healthy, immunocompetent males or females at least 2 years of age or older for Cohort 1 and 12 years and older for Cohort 2.
2. Present with 1-6 common warts (*verruca vulgaris*) located anywhere on the body except for the following prohibited areas: the eye area (including eyelids), lips, oral cavity, nasal cavity, inside of the ears, palms of the hands, volar surface of the fingers or toes, under the finger nails (near and on the sides of the nails is allowed for Cohort 1, but warts near and on the sides of the nail (e.g., periungual) are not allowed in Cohort 2), soles of the feet, or the anogenital area. (*Warts within 10 mm of a mucosal surface should not be treated*).
3. Have warts that are ≤ 10 mm in diameter and ≤ 3 mm in height. (*Subjects with warts that are adjacent, touching or clustered may be included so long as the combined diameter in the longest direction does not exceed 10 mm. Individual lesions that are adjacent, touching or clustered should be counted as distinct lesions for the purposes of tracking, inclusion and clearance*)(*subjects in Cohort 2 can be pared, when necessary and appropriate, prior to evaluating height eligibility, See manual of operations for details*).
4. All warts must be present for at least 4 weeks at baseline visit.
5. Consent to having all warts treated (the physician must also be willing to treat all warts initially present).
6. Be otherwise medically healthy with no clinically significant medical history, physical examination or vital signs as determined by the investigator.

7. Are free of any systemic or dermatologic disorder, which, in the opinion of the investigator, will interfere with the study results or increase the risk of AEs.
8. Refrain from swimming, bathing or prolonged immersion in water or any liquids until the Study drug is removed.
9. Have the ability, or have a guardian with the ability, to follow study instructions and be likely to complete all study requirements.
10. Agree to use no wart-removing product (prescription or over-the-counter [OTC]) other than the Study drug during the course of the study.
11. Provide written informed consent or assent in a manner approved by the institutional review board (IRB) and/or have a parent/guardian provide written informed consent as evidenced by the signature on an IRB approved assent/consent form.
12. Provide written authorization for use and disclosure of protected health information.
13. If participating in the optional photos portion of the study: Agree to allow photographs of warts to be taken at each Treatment Visit by the research team and agree to share photos taken at home with the research team via text, email or in-person upload.

4.2.2 Exclusion Criteria

Candidates will be excluded from the study if they:

1. Are unable to cooperate with the requirements or visits of the study, as determined by the investigator.
2. Are systemically immunosuppressed or have required, or will require, systemic immunosuppressive or immunomodulatory medication (including oral or parenteral corticosteroids) within 30 days prior to enrollment or during the course of the study. (Routine use of inhaled or intranasal corticosteroids during the study is allowed.)
3. Have any chronic or acute medical condition that in the opinion of the investigator, may interfere with the study results or place the subject at undue risk. (e.g., human immunodeficiency virus, systemic lupus erythematosus, viral hepatitis, uncontrolled diabetes). NOTE: Immunizations and flu shots may be administered throughout the study, but not within 5 days before or after treatment.
4. Have more than 6 common warts at baseline.
5. Present with any verruca plana, mosaiform, filiform, subungual (under the nail), genital or anal warts. In Cohort 2, subjects with periungual warts are also excluded.
6. Have any warts present at baseline in an anatomic location the subject, parent/guardian or the physician is unwilling to treat or are located in an area that cannot be easily occluded tape.
7. Have had any previous treatment of common warts including but not limited to the use of cantharidin, antivirals, retinoids, salicylic acid, lactic acid, hydrogen peroxide, candida antigen, diphencyprone, dinitrochlorobenzene, sandalwood oil, thuja oil, squaric acid dibutyl ester, povidone iodine, curettage or freezing of warts in the past 14 days. In addition, these treatments or any other over-the-counter wart treatment should not be implemented during the course of the study.

8. Have been treated within 14 days with a product that contains cantharidin (topical or homeopathic preparations) for any reason prior to screening.
9. Have received another investigational product as part of a clinical study within 30 days prior to the first application of the Study drug.
10. Currently have, or have a history of, epidermodysplasia verruciformis.
11. Have a history of illness or any dermatologic disorder which, in the opinion of the investigator, will interfere with accurate assessment of the warts or increase the risk of adverse events.
12. Have an active malignancy or are undergoing treatment for any malignancy.
13. Have a history or presence of clinically significant medical, psychiatric, or emotional condition or abnormality that, in the opinion of the investigator, would compromise the safety of the subject or the quality of the data.
14. Have a history or presence of hypersensitivity or an idiosyncratic reaction to the Study drug or related compounds, or drug product excipients (acetone, ethyl alcohol, nitrocellulose, hydroxypropyl cellulose, castor oil, camphor, gentian violet, and denatonium benzoate).
15. Have a condition or situation that may interfere significantly with the subject's participation in the study (e.g., subjects who required hospitalization in the 2 months prior to screening for an acute or chronic condition including alcohol or drug abuse), at the discretion of the investigator.
16. Are sexually active or may become sexually active and are unwilling to practice responsible birth control methods. (e.g., combination of condoms and foam, birth control pills, intrauterine device, patch, shot and vaginal ring, etc.). Withdrawal is not an acceptable method of birth control. Females that have reached menarche must have a negative urine pregnancy test at each visit prior to treatment with Study drug.
17. Are pregnant or breastfeeding

